#### **4.2. Randomization and Masking**

A confidential computer-generated simple randomization scheme (using STATA 16, Dallas, TX) has been prepared. A randomization log with group assignment, subject name, and medical record number will be used to track the randomization process.

Subjects will be randomized in a ratio of 1:1 for delayed or early amniotomy.

Due to the nature of the intervention, blinding of subjects or providers will not be possible.

The subject will be included in the analysis by intent-to-treat once the randomization assignment has been made.

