### **3. Concise Summary of Project:**

- The target population for our study is both nulliparous and parous women who present for induction of labor. If there is a decision by the obstetric team to place a transcervical Foley balloon for cervical ripening, the obstetric team will notify the research team so that the patient may be screened for the study. If the subject consents to participation, written informed consent will be obtained by person-to-person contact. The PI or a collaborator will be responsible for the informed consent. After informed consent is obtained, the transcervical Foley balloon will be placed. The method of placement will be left to the discretion of the provider. After placement of the Foley balloon, the subject will be randomized to the study group (early amniotomy) or the control group (delayed amniotomy).

The control group will undergo amniotomy at least four hours after expulsion of the Foley balloon.

The study group will undergo amniotomy as soon as possible after Foley balloon expulsion or within two hours of expulsion.

At any point, if the treating provider determines amniotomy is unsafe, amniotomy may be delayed and performed as soon as the provider deems safe.

This will be an unblinded randomized clinical trial.

No significant adverse effects are expected with the use of amniotomy. The most significant risks associated with amniotomy are fetal heart rate decelerations, ascending infection, umbilical cord prolapse (<1%), rupture of vasa previa (<1%). The subject will undergo inpatient induction of labor, so any adverse reaction would be promptly detected and addressed.

- The number of subjects studied will be 174 subjects at UTMB. The subjects will be withdrawn from the study if she wishes to discontinue participation. If any of the exclusion criteria listed above are met, or there is a change in condition that leads to inclusion

criteria no longer being met, data collection will be terminated and the subject will be withdrawn from the study.

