## Study Summary Flow Diagram

#### 4.9. Primary Outcomes

- Time interval from Foley balloon placement to reaching the active phase of labor (6 cm cervical dilation)

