## 13. Statistical Approach

Analysis will be performed by intent to treat. Univariable and multivariable analysis will be used to describe the population in the study and to identify potential confounding variable. For this analysis normality will be tested using Shapiro-Wilk method. Demographics and descriptive statistics such as t test, Pearson's chi square, and Mann-Whitney tests will be used as indicated. Data will be either shown as median +/- Range or mean +/- SDEV. Statistical analyses of primary and secondary outcomes between two groups will be performed by multivariate logistic regression analysis accounting for confounding variables if indicated.

Based on our prior results (DILAFOL Trial), women who received Foley balloon and delayed amniotomy reached active phase of labor in 1111 mins with a standard deviation of 525 mins. Using difference rate of 25%, power of 90% and 2-sided alpha of 0.05, we estimate that we will need 150 with complete ascertainment. This difference of 278 or ~4hours was decided after consulting clinical experts in the field of obstetrics, supporting clinical reasoning that a difference between both methods is clinically significant. Detailed from stata 16 : Estimated sample sizes for a two-sample means test (z test) ;Study parameters: alpha = 0.0500; power = 0.9000; delta = -278.0000; mean1 = 1111.0000; mean2 = 833.0000 sd = 525.0000 Estimated sample sizes: N = 150

N per group = 75. Assuming a 13% loss to follow, we propose to enroll a total of 174 subjects. Analyses will be performed by intent to treat. We will be using STATA 16 (Dallas, TX) for statistical computations

This trial will be registered with Clinical Trials Register (Clinicaltrials.gov), before recruitment is initiated and after IRB approval.

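### Parity is neither a randomization stratum nor a pre-specified covariate in a trial that enrols both nulliparous and parous women, which gives up precision and protection against chance imbalance

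*Combined protocol and SAP*

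**What the plan says.** Section 3 sets the population: "The target population for our study is both nulliparous and parous women who present for induction of labor". Sections 6 and 7 add no parity restriction. Section 4.2 gives the allocation method, "A confidential computer-generated simple randomization scheme (using STATA 16, Dallas, TX) has been prepared", and the ratio, "Subjects will be randomized in a ratio of 1:1 for delayed or early amniotomy". No stratification, blocking or minimization appears anywhere in the document.

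The primary outcome in Section 4.9 is a duration: "Time interval from Foley balloon placement to reaching the active phase of labor (6 cm cervical dilation)". Section 13 sizes the trial by an unadjusted two-sample comparison of means, from women who "reached active phase of labor in 1111 mins with a standard deviation of 525 mins".

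The only provision for covariates is also in Section 13. It plans univariable and multivariable work to find potential confounders, then a logistic regression for primary and secondary outcomes that adjusts for them where this is judged necessary. Parity is not named there, and no analysis by parity is described.

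**The concern.** Parity is known before randomization, is binary, and could plausibly affect how long a woman takes to reach 6 cm. The eligibility criteria deliberately leave it open. The protocol's own references treat it as a design variable: one of the early-amniotomy trials it cites is, by its title, confined to nulliparous induction. Section 1 also faults earlier work for mixing ripening methods and asks for that source of variation to be controlled, while parity is left uncontrolled.

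Two things are at stake. First, if the arms happen to differ in parity, the crude difference in minutes moves with that imbalance, and so may the crude cesarean and vaginal-delivery comparisons. The plan then offers only an adjustment chosen after the data are seen, in an open-label trial. The logistic model it names would not estimate a difference in minutes in any case. Second, even with balanced arms, leaving parity out of the model keeps its variance in the error term, so power that costs nothing in recruitment goes unused.

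**Working it through.** **Inputs from the documents.** 174 enrolled (Section 3); 150 evaluable, SD 525 min, difference 278 min, 90% power, two-sided alpha 0.05 (Section 13).

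**Assumptions, because the documents give neither figure.** Nulliparous share p of 30-70%; difference D in mean time to 6 cm between nulliparous and parous women of 200-400 min; overall SD held at 525 min.

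**1. The plan's own figure.** n per arm = 2 × (1.960 + 1.282)² × 525² / 278² = 74.9, so 75 per arm and 150 in total. Inflating for 13% loss, 75 / 0.87 = 86.2, so 87 per arm and 174 in total. Both figures reproduce.

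**2. How often parity is imbalanced.** The SD of the between-arm difference in nulliparous share is about √(p(1−p) × 4/174). This is 7.6 points at p = 50% and 6.9 points at 30% or 70%. Simulating simple 1:1 allocation of 174 women gives an SD of 7.0-7.6 points, and:

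| Nulliparous share (assumed) | Difference ≥ 10 points | Difference ≥ 15 points |
|---|---|---|
| 30% or 70% | 15% | 3% |
| 50% | 20% | 5% |

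**3. What an imbalance does to the crude difference.** Shift = imbalance × D. The low end is 0.10 × 200 = 20 min and the high end is 0.15 × 400 = 60 min. Against the target, 20/278 = 7% and 60/278 = 22%.

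The sampling error of the comparison is the fairer yardstick. At N = 174 the standard error is 525 × √(4/174) = 80 min, so the shift is 20/80 = 0.25 to 60/80 = 0.75 standard errors. At N = 150 the standard error is 525 × √(4/150) = 86 min, and the ratio is 0.23 to 0.70.

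**4. What adjustment gains.** With parity in a linear model, residual SD = √(525² − p(1−p)D²). At 150 evaluable women and p = 50%, power is Φ(278/SE − 1.96), where SE = residual SD × √(4/150):

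| D (assumed) | Residual SD | SE | Power |
|---|---|---|---|
| parity not in model | 525 | 85.7 | 90.0% |
| 200 min | 515 | 84.2 | 91.0% |
| 400 min | 485 | 79.3 | 93.9% |

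**5. What stratifying adds.** With blocks of 4 within each parity stratum (an illustrative size), the worst case is a surplus of two women in one stratum and the reverse in the other. The nulliparous shares then differ by 2/87 = 2.3 points, against a 95% range of about ±14 to 15 points under simple randomization. For power the extra gain is small. In simulations with 150 women, half nulliparous, power was as follows:

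| D (assumed) | Simple, unadjusted | Simple, adjusted | Stratified, adjusted |
|---|---|---|---|
| 200 min | 89.3% | 90.2% | 90.9% |
| 400 min | 89.5% | 93.5% | 93.7% |

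Type I error was 4.9-5.4% throughout.

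**The case against.** The strongest reply is that nothing here is an error. Simple randomization is a legitimate choice, and chance differences in parity are already counted in the standard error when the SD is the overall SD. That stands.

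A reader might infer that the primary comparison is biased or its type I error inflated. Conditional figures encourage this. For an assumed parity effect of 278 min, 150 evaluable women (half nulliparous) and an imbalance at the 95% limit, type I error is 7.3%, and power is 79% if the imbalance is unfavourable. These describe one unlucky allocation; over all allocations the type I error stays at 5%. The documents do not support a charge of bias.

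A reader might also infer that the 75 per arm in Section 13 is unsafe because simple randomization does not fix arm sizes. The effect is immaterial: a 65/85 split gives 89.5% power instead of 90.0%.

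It can be said, too, that Section 13 already allows adjustment. It does, which is partial mitigation, but it neither names parity nor commits to adjusting, and the model it names does not suit a duration.

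Finally, simple randomization is the least predictable scheme, which has value in an open trial at one site where earlier assignments are visible. That is a fair reason for the choice, and stratified blocks are therefore not free. It is no reason to leave parity out of the model, which delivers most of the gain in power.

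**Conclusion.** The point holds as a matter of precision and of protection against chance imbalance. Simple, unstratified allocation of a mixed-parity population, combined with an adjustment that is optional and does not name parity, leaves a 15-20% chance of an imbalance of at least 10 points. A 10-15 point imbalance would shift the crude difference by 20-60 min, well short of the 278-min target and under one standard error. It also leaves about 1 to 4 points of power unused at 150 evaluable women.

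The imbalance probabilities rest on the assumed 30-70% nulliparous share, and the size of the shift also on the assumed 200-400 min parity effect. The power gain further assumes a linear model and an even parity mix. The documents give neither the mix nor the effect, so a smaller parity effect would shrink both the shift and the gain. The stated sample size reproduces and need not change.

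**What to change.** **In Section 13**, name parity (nulliparous versus parous) as a covariate in the primary model for time to 6 cm. State that it will be included regardless of observed imbalance, and replace logistic regression for this outcome with a linear or time-to-event model. The power figures above apply to the linear model, which matches the difference in minutes used for the sample size. The cost is a sentence or two and one variable taken from the chart. This remains available after enrolment has begun, provided it is fixed before the data are analysed.

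**In Section 4.2**, only if no woman has yet been randomized, replace the prepared list with one stratified by parity, using block sizes that vary at random and are not disclosed to enrolling staff. Section 13 places registration ahead of recruitment and still in the future, so this appears possible as the document is written. The cost is one regenerated list, one changed sentence and somewhat more predictable assignments, which undisclosed varying blocks limit. Parity imbalance would be nearly, not wholly, removed: a few points can remain from incomplete blocks, and losses can add to that in the evaluable set.

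If randomization has started, leave the list alone; the covariate is then sufficient.

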#### **4.3. Amniotomy**

The control group will undergo delayed amniotomy. At least four hours after Foley balloon expulsion, the provider will perform amniotomy using a plastic amniotomy hook. After amniotomy, standard intrapartum management of the subject will ensue.

The study group will undergo early amniotomy. The provider will perform amniotomy as soon as possible after Foley balloon expulsion or within two hours of expulsion. After amniotomy, standard intrapartum management of the subject will ensue.

If the provider feels the amniotomy is unsafe (floating or ballotable presenting part, head not engaged in the pelvis), amniotomy will be performed as soon as it is deemed safe. If amniotomy is performed outside of the time limits outlined, the subject will remain in the study since we will perform an intent-to-treat analysis.

Foley balloon placement is standard of care in our facility for cervical ripening. Decision for its placement will be solely left to provider's discretion. Both groups will have a foley balloon placed as per standard protocol in our institution.

Oxytocin infusion will be left to provider's discretion based on our unit's standard of practice.

#### **4.4. Baseline Procedures**

Routine intrapartum care will be provided by the subject's managing obstetric team.

Trained and experienced research staff will be responsible for all research data abstraction.

The PI and collaborators will review and validate the diagnosis for all subjects identified to have the primary outcomes.

Maternal and neonatal outcomes will be assessed following delivery.

Subjects will be encouraged to call the principal investigator with any concerns.

Data collection forms will be used during these processes and charts will be reviewed up to 30 days postpartum. We will collect demographic data, as well as data related to the subject's intrapartum course, delivery, and immediate postpartum period while inpatient. Data on newborn status, including those admitted to the NICU, will be obtained from the infants' charts.

Subjects' participation will end after being discharged home from the hospital.

[figure not shown]
#### **4.5. Study visits / Follow-up**

No additional postpartum follow-up visits will be performed.

#### **4.6. Withdrawals**

Subjects who withdraw from the study after randomization will be excluded from further follow-up. Outcomes ascertained up until the time of withdrawal will be reported in intent-to-treat fashion.

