**7. Criteria for Exclusion of Subjects**

- Previous uterine surgery
- Prelabor rupture of membranes
- Severe pre-eclampsia, HELLP, or eclampsia
- HIV, HCV, or HBV
- Heart disease
- Fever ( $\geq 38^{\circ}\text{C}$ ) at admission
- Category II or III fetal heart rate tracing prior to randomization
- Polyhydramnios
- Fetal growth restriction  $<3\%$
- EFW  $> 4200$  g
- Fetal demise or major congenital anomaly
- Prisoners

**8. Sources of Research Material:** Electronic medical chart / records

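### Section 4.6 ends follow-up when a randomized woman chooses to withdraw, so later outcomes that the routine chart would still supply are lost, possibly unequally by arm

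*Combined protocol and SAP*

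**What the plan says.** All references are to the combined protocol and SAP.

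- **Who is withdrawn.** Section 3: "The subjects will be withdrawn from the study if she wishes to discontinue participation".
- **What then happens.** Section 4.6: "Subjects who withdraw from the study after randomization will be excluded from further follow-up". Its next sentence limits the effect: "Outcomes ascertained up until the time of withdrawal will be reported in intent-to-treat fashion".
- **Analysis principle.** Section 4.2: "The subject will be included in the analysis by intent-to-treat once the randomization assignment has been made". Section 13 repeats intent to treat. For incomplete data it offers only a 13% enrollment allowance, with no method for a missing time to 6 cm.
- **Departures from the assigned timing.** Section 4.3: "If amniotomy is performed outside of the time limits outlined, the subject will remain in the study". Section 10 handles departures from assignment as protocol deviations, reported by providers or found in the chart.
- **Where data come from.** Section 8 lists one source: "Electronic medical chart / records". Section 4.5 adds no postpartum visits. In Section 4.4, "charts will be reviewed up to 30 days postpartum", although the same section ends participation at discharge. The plan therefore already reads charts after participation is over.

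No section separates a woman who no longer wants the assigned timing, or no longer wants to take part, from one who refuses further use of her records.

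**The concern.** After randomization the trial asks one thing of the woman: the timing of her amniotomy. Everything else is routine care, recorded whether or not she is in a study. She can give up the assigned timing and still contribute every outcome, yet under Section 4.6 any withdrawal ends collection.

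The primary outcome is exposed. Randomization follows Foley placement, and the interval to 6 cm has a planning mean of 1111 minutes (about 18.5 hours) in the delayed arm. There is ample time to withdraw before the outcome occurs. Cesarean, infection and neonatal outcomes come later still.

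The loss could also differ by arm. Assignment is known to everyone. After balloon expulsion, amniotomy is planned within two hours in one arm and after at least four in the other, so the delayed arm has a longer period in which there is still an assigned timing to decline. If the women who leave also labor more slowly or faster than those who stay, the observed arm means shift by different amounts. Losing slow women from the delayed arm shrinks an apparent benefit of early amniotomy; losing them from the early arm exaggerates it.

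**Working it through.** **1. The plan's own figure (Section 13).** Inputs: difference 278 min (1111 against 833), SD 525 min, two-sided alpha 0.05, power 90%, 1:1 allocation.

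n per arm = 2 × (1.960 + 1.282)² × (525/278)² = 2 × 10.51 × 3.566 ≈ 75, so 150 in total. With 13% loss, 75/0.87 = 86.2, rounded up to 87 per arm, or 174. Both stated figures reproduce. Power is 90.0% with 150 women ascertained and 93.7% with all 174.

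**2. Which outcomes Section 4.6 loses for a woman who withdraws by choice**

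| Time of withdrawal | Time to 6 cm | Delivery, maternal and neonatal outcomes |
|---|---|---|
| Before 6 cm | Not observed | Later ones not collected |
| After 6 cm, before delivery | Kept | Later ones not collected |
| After delivery | Kept | Earlier ones kept, later ones not collected |

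**3. Possible effect on the difference in means.** The documents give neither a withdrawal rate nor the prognosis of women who withdraw, so both are assumed. Let f be the fraction of an arm that withdraws before 6 cm, and let these women be k SD slower, with k = 0.5 to 1. The observed arm mean is too short by:

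- (a) f × k × 525, if k is measured against the women who stay;
- (b) f/(1 − f) × k × 525, if k is measured against the whole arm.

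The bias in the comparison is the difference between the two arms' shifts.

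| Loss before 6 cm, one arm vs the other | (a) k = 0.5 to 1 | (b) k = 0.5 to 1 | Share of 278 min |
|---|---|---|---|
| Equal, similar women (e.g. 13% vs 13%) | 0 | 0 | 0% |
| 5% vs 0% | 13.1 to 26.2 | 13.8 to 27.6 | 5 to 10% |
| 13% vs 5% | 21.0 to 42.0 | 25.4 to 50.8 | 8 to 18% |
| 13% vs 0% | 34.1 to 68.2 | 39.2 to 78.4 | 12 to 28% |

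Examples, 5% vs 0% with k = 1: (a) 0.05 × 525 = 26.2; (b) 0.05/0.95 × 525 = 27.6. For 13% vs 5% under (b) with k = 1: (0.1494 − 0.0526) × 525 = 50.8.

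**4. Effect on the test.** With 87 randomized per arm and formula (a), the standard error at 5% vs 0% is 525 × √(1/82.65 + 1/87) = 80.6 min. A bias of 13.1 to 26.2 min raises the two-sided type I error from 5% to between 5.3% and 6.2%. At 13% vs 5% it is 5.7 to 7.9%, and at 13% vs 0% it is 7.0 to 13.1%.

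**The case against.** The case on the other side is substantial, and much of it limits the point.

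- **Data are kept up to withdrawal.** A reader might infer from the first sentence of Section 4.6 that a withdrawn woman's outcomes are thrown away. The second sentence rules that out; only later outcomes are lost.
- **Mistimed amniotomy does not remove anyone.** Section 4.3 gives no limit on the reason, and Section 10 treats departures as deviations. Neither Section 3 nor Section 4.6 says that declining the assigned timing counts as withdrawal. This stands, but a woman who says she wants to stop falls under Section 3, and staff are not told to ask what she wants stopped.
- **Unobserved events.** A reader might infer that a cesarean or infection after withdrawal would be counted as not having happened. Nothing says so, and Section 13 plans for 150 women with complete ascertainment, which fits treating the rest as missing. The plan is silent.
- **Intent to treat.** It is tempting to say that Section 4.6 breaks the promise in Section 4.2. It does not change the analysis set; it creates missing outcomes within it.
- **Bias is not shown.** Every woman in the delayed arm faces the four-hour wait, and it starts after balloon expulsion, so the wait is not itself a sign of slow labor. That slow inductions prompt withdrawal is conjecture.
- **Consent.** The consent pages are not available for review and may already cover continued chart use. Stopping collection when a woman ends participation is also a defensible reading of voluntary participation. For women who refuse use of their records, that is right and the fix leaves it alone.

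What survives is that the plan offers no continued abstraction to women who would permit it.

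**Conclusion.** The point holds as an avoidable source of missing data with a possible, undemonstrated bias. Outcomes after voluntary withdrawal go uncollected although the chart would supply them, and a woman who leaves before 6 cm has no primary outcome.

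On the assumptions above, one-sided 5% withdrawal of women 0.5 to 1 SD slower moves the estimate by about 13 to 28 min, a modest share of the target difference, with little effect on type I error. The 34 to 78 min range is an extreme scenario. It needs 13% lost before 6 cm from one arm and none from the other, and Section 13's 13% is an allowance for loss of every kind; a reader should not take it as an expected withdrawal rate.

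Section 3 also has a rule for loss of eligibility, under which "data collection will be terminated and the subject will be withdrawn from the study". That is a different mechanism, and this conclusion does not rest on it.

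**What to change.** Amend Section 4.6, and the matching sentence in Section 3, to say in substance:

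1. A randomized woman who no longer wishes to follow the assigned amniotomy timing, or to take part, stays in her assigned group for analysis. Chart abstraction of all primary, secondary and safety outcomes continues to the planned end of data collection, unless she withdraws permission to use her records.
2. If she withdraws that permission, collection stops, the time and reason are recorded, and outcomes not yet observed are treated as missing.

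Staff should ask which of the two she means, and the report should give both counts by arm. Her clinical care is unaffected.

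The cost is IRB review of the protocol and consent wording, a short question to women who ask to stop, and one extra field on the data form. No additional visits or patients are needed, and the sample size does not change.
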